During FY 2012, 391 patients with implanted port catheters were treated in the OPCC. Seventy of these patients experienced an occlusion of their port that required the administration of alteplase (CathFlo) ([name], personal communication, October 12, 2012). Thus, 70 of 391 experienced an occlusion resulting in an occlusion rate of 18%. Some of these 70 patients experienced an occlusion more than once during that time. Additionally, during that time, a few patients had their implanted port catheters removed due to infection or malfunction. The exact number of patients who experienced multiple occlusions or had their implanted ports removed/replaced during FY2012 is unknown.

During the planning of the current study evaluating implanted port catheters, we engaged the consultation of a biostatistician through the Center for Clinical and Translational Science and Training (CCTST) to conduct a power analysis to

establish the number of participants needed in each group to determine the non-inferiority of the alternative therapy (saline only flush). Consultation was provided by [name], Associate [name] Hospital Medical Center, University of Cincinnati.

Based on the literature and our own experience we estimated an approximate occlusion rate of 20% with the standard treatment (saline + heparinized saline flush as described above). The power analysis conducted by [name] determined that, using a two group normal approximation test of proportions with a one-sided .05 significance level, a sample size of 198 participants per group will have 80% power to reject the null hypothesis that the proposed method is not inferior (i.e. the difference in proportions between the proposed method and the standard method is greater than 0.10). Thus, we will continue to recruit participants in that study until 198 have been enrolled in each group for a total of 396 study participants.

[name] was consulted again when the introduction of the BioFlo Port at TriHealth was discovered. It is [name] recommendation that this second randomized controlled trial using the same methodology and power analysis calculations be conducted. Thus, we will recruit 198 participants per group for a total of 396 participants in this study.

Data Collection:

Independent Variables: Method for flushing implanted port catheters:

- 20 mL of saline followed by 5 mL of Heparinized saline in a concentration of 100 units/mL
OR
- 20 mL of saline only

Dependent Variables:

Primary Outcomes

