- Occurrence of first complete (can neither withdraw blood nor flush the catheter) occlusion
- Occurrence of first partial (able to flush but unable to withdraw blood) occlusion
- Frequency with which alteplase (CathFlo) has to be utilized to resolve an occlusion

Secondary Outcomes

- Number of subsequent occurrences of complete or partial occlusions after the first occurrence.
- Amount of time in days that a port remains patent (flushes easily and able to obtain a blood return).
 - Amount of time between entrance in study and first incidence of partial or complete occlusion

- Amount of time between incidences of partial or complete occlusion.
- Occurrence of other complications:
 - Central Line-Associated Blood Stream Infection (CLABSI) – a laboratory-confirmed (recognized pathogen cultured from one or more blood cultures; organism cultured from blood is not related to an infection at another site) blood stream infection that is considered central line associated (CDC, 2012).
 - Develops complication related to Heparin
 - HIT (Heparin induced thrombocytopenia as measured by a positive HIT antibody test)
 - Other heparin allergy

Moderating variables: other things that could also affect patency of the port

- Number of times port flushed per month or frequency of flushing.
- Use of prophylactic doses of anticoagulant drugs (e.g., enoxaparin, heparin, warfarin)
- Development of a hypercoaguable state, as diagnosed by primary hematologist/oncologist
- Mechanical difficulties related to port placement e.g. “Pinch-off syndrome”
- Length of time port has been in place prior to entrance in study

Extraneous variables:

- Type of cancer
- Age of participant

Data collection tool

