Statistical Analysis: Descriptive statistics will be used to describe the participants. Differences between groups on the dependent variables will be calculated using t-test, Chi-Square or Fisher's exact test as appropriate for the level of data under analysis (also see discussion regarding interim analysis). Regression analysis will be used to determine the effect of the moderating variables on the occurrence of occlusion in the implanted ports. Participants in the

control group and intervention group will be further stratified based on frequency of port flushing. Differences in the rate of occlusion between stratified groups will also be calculated.

Ethical Considerations: The purpose of this study is to determine the safest and most effective flushing solution(s) for maintaining patency in implanted port catheters. In so doing, study participants could be placed at potential risk for catheter occlusion. All catheter occlusion will be treated according to TriHealth policy, i.e., the instillation of alteplase (CathFlo) (see Appendix A). Potential study participants will be made aware of the risk when enrolled in the study (See Appendix B) script for recruiting patients into the study and the Informed Consent Statement).

Informed Consent: Patients who meet inclusion criteria will be approached by a member of the research team who will explain the study, implications of their participation and review the Informed Consent Statement and HIPAA Authorization Forms (see the attached). One signed copy of the Informed Consent Form and HIPAA forms will be given to the study participant and another placed in their folder in the TriHealth Infusion Center to be scanned into their EPIC electronic health record (EHR). The original signed Informed Consent Statement and HIPAA will be stored in a locked drawer in a TriHealth office until the study is completed and closed with the IRB. The RN seeking consent and PI will document the informed consent process in the participant's EHR. Additionally, the blue or yellow sticker on the patient folder in the treatment center and presence of data collection forms in the patient folder will indicate that the patient is a participant in the study.

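### The occlusion comparison is unadjusted although candidate baseline predictors are already collected, so a modest, nearly free gain in precision may be forgone; the crude comparison itself is valid.

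*Combined protocol and SAP*

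**What the plan says.** Under Statistical Analysis the arms are compared without covariates: "Differences between groups on the dependent variables will be calculated using t-test, Chi-Square" or Fisher's exact test, according to the type of data. The same section adds a second analysis, "Regression analysis will be used to determine the effect of the moderating variables on the occurrence of occlusion in the implanted ports", and a comparison within strata of flushing frequency. Neither is said to include study arm or to supply the non-inferiority estimate.

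The moderating variables listed under Data Collection are described only as things that may influence patency. Some can be fixed at entry, such as "Length of time port has been in place prior to entrance in study" and prophylactic anticoagulant use. Others arise after randomisation: how often the port is flushed, and development of a hypercoagulable state. Cancer type and age are listed separately as extraneous variables.

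The Data collection tool section says the Face Sheet records age, gender, cancer type, hypercoagulable diagnosis or history, anticoagulant use, single or double port, and insertion date. It is completed at enrolment and updated as events become known.

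Allocation, under Recruitment, is by sequentially numbered opaque sealed envelopes. No stratification factors are described.

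**The concern.** The investigators name factors that may affect occlusion and collect them, but the treatment comparison uses none of them. If some do predict occlusion, a comparison that takes account of them has a smaller standard error, and so a tighter upper limit to set against the margin, with no extra participants.

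There is also a question of which adjusted result would be reported. The planned regression draws on a list that mixes entry characteristics with post-randomisation ones. If its output were later presented as the adjusted treatment effect, it would condition on variables that can be affected by what happens after allocation. Fixing the covariate set in advance removes that ambiguity.

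**Working it through.** **1. The plan's own figure.** The inputs are in the power calculation under Recruitment:

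- control rate: "we estimated an approximate occlusion rate of 20% with the standard treatment";
- test: "using a two group normal approximation test of proportions with a one-sided .05 significance level";
- margin: "the difference in proportions between the proposed method and the standard method is greater than 0.10";
- result: "a sample size of 198 participants per group will have 80% power".

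A true difference of zero is not stated, so I assume it.

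n per group = (1.645 + 0.842)² × 2 × 0.20 × 0.80 / 0.10² = 197.84, rounded up to 198. The figure reproduces. (The historical rate of 70/391 = 17.9% would give 182, so 20% is the input used.)

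**2. Crude comparison.** SE = √(2 × 0.20 × 0.80 / 198) = 0.0402. Power = Φ(0.10/0.0402 − 1.645) = 80.0%.

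**3. Adjusted comparison.** If entry covariates explain a share R² of outcome variance, the variance is multiplied by about (1 − R²). For R² = 0.05: SE = 0.0402 × √0.95 = 0.0392, and power = Φ(0.10/0.0392 − 1.645) = 81.8%. R² is not in the documents; the range is assumed.

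| Assumed R² | SE | Power at 198 per group | n per group for 80% |
|---|---|---|---|
| 0 | 0.0402 | 80.0% | 198 |
| 0.02 | 0.0398 | 80.7% | 194 |
| 0.05 | 0.0392 | 81.8% | 188 |
| 0.10 | 0.0381 | 83.6% | 179 |

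**4. Cost of estimating coefficients.** The formula in step 3 ignores this cost. About 396 × 0.20 = 79 events are expected. I simulated a standardised risk difference from a logistic model (198 per arm, 20% risk, combined baseline score with log-odds SD 0.4, 0.6 or 0.8, corresponding to R² of about 2.5%, 5% and 9%). The ratios of adjusted to crude variance were:

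| Covariate terms | No signal | SD 0.4 | SD 0.6 | SD 0.8 |
|---|---|---|---|---|
| 3 | 1.01 | 0.98 | 0.95 | 0.90 |
| 10 | 1.03 | 1.01 | 0.99 | 0.95 |

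A repeat with a different seed gave the same no-signal costs and ratios within 0.04 elsewhere, so these figures are approximate. A variance ratio of 1.01 corresponds to power of Φ(0.10/(0.0402 × √1.01) − 1.645) = 79.7%. A short list therefore risks about 0.3 of a power point.

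**5. Validity of the crude comparison.** I ran 40,000 simulated trials per setting, with one binary baseline factor that changed risk by 10, 20 or 30 points.

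- The crude estimate averaged 0.000 at a true difference of 0 and 0.100 at the margin.
- One-sided error at the margin was 4.9% to 5.0% crude and 4.9% to 5.2% adjusted (post-stratified).
- With 50% prevalence of the factor, adjusted power was 80.3%, 82.3% and 85.1%, against about 80% crude.

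**6. What chance imbalance amounts to.** Assume a factor with 20% prevalence and a 15-point effect on risk. The SD of the between-arm imbalance is √(2 × 0.2 × 0.8 / 198) = 0.0402, so a 2-SD imbalance is about 8 points. The crude difference then moves by 0.08 × 0.15 = 1.2 points, or 1.2/4.02 = 0.30 of a standard error. The factor's R² is 0.15² × 0.16 / 0.16 = 0.0225. This is the same variance that step 3 removes.

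**The case against.** The strongest reply is that an unadjusted test is a legitimate choice, matched to its own sample-size calculation, and that nothing here is an error. That stands. Several supporting points also stand:

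- No association, odds ratio or R² appears in the documents, so the gain cannot be derived from them. Eligibility requires a port in place less than one year and excludes therapeutic anticoagulation, which limits the spread of two obvious candidates.
- A long covariate list would give back most of the gain (step 4).
- The Face Sheet is updated during follow-up. Whether entry values can be separated from later entries depends on Appendix C, which I have not seen.
- Statistical Analysis names tests of difference and sets no confidence limit against 0.10. Supplying that limit matters more than adjustment and can be done with the crude estimate. It should not be credited to adjustment.

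A reader might also infer something stronger: that strong predictors have been ignored, or that uncontrolled imbalance biases the non-inferiority estimate. The documents do not support either. They say only that the moderators may matter. Chance imbalance is already part of the crude standard error. It is true that non-inferiority needs an observed difference below about 0.10 − 1.645 × 0.0402 = 0.034, so a 1.2-point shift is about a third of that room. But counting this shift as well as the precision gain would count the same variance twice. Nor do the documents say that the envelope list was simple rather than blocked.

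**Conclusion.** This is an optional improvement in efficiency. The planned crude comparison is unbiased, keeps its error rate and has its stated 80% power under the plan's assumptions. Adjustment for a few entry-time covariates would raise power to about 81% to 84% if they explain 2% to 10% of outcome variance; that range is assumed. If they explain nothing, the variance rises by about 1%. The planned moderator regression does not already provide this, because it is not said to include arm and its covariate list includes post-randomisation variables. As a secondary explanatory analysis, it does no harm to the primary comparison.

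**What to change.** Before analysis, pre-specify the primary estimate for the occlusion outcome to which the 0.10 margin applies:

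- Use a standardised (marginal) risk difference from a logistic model with group and three or four covariates, for example port dwell time, prophylactic anticoagulant use, hypercoagulable history (each at entry) and age. An odds ratio would not be on the scale of the margin.
- Compare its one-sided 95% upper limit with 0.10, and report the crude risk difference and its limit alongside.
- Use only values recorded at enrolment. Exclude flushing frequency and any hypercoagulable state that develops later, and leave these to the moderator regression, labelled exploratory.
- Confirm that entry values on the Face Sheet can be told apart from later updates, and drop any covariate for which they cannot.

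The cost is plan wording, a few lines of code and that one check. It needs no extra participants, and no new data if the check succeeds.

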While evidence in the literature is scant, there is no clear consensus on the need and efficacy of heparinized saline as the solution for maintaining patency in implanted port catheters (Camp-Sorrell, 2010). Therefore, a nursing research study to determine the safest and most effective flushing solution(s) for maintaining patency in implanted port catheters began in the TriHealth Infusion Centers in January of 2013. This is an ongoing non-inferiority study using a randomized controlled trial methodology to compare the efficacy to a 20 mL normal saline flush with a 20 mL normal saline flush followed by a 5 mL heparinized saline (100 units/mL), the standard of care at TriHealth. As of October 30, 2015, 135 of 396 target population have been enrolled in the study.

A few months ago, the BioFlo Port with Endexo Technology (referred to hereafter as the BioFlo Port) was introduced in some of the TriHealth facilities inserting implanted port catheters and providing care to patients with implanted port catheters. The catheter in the BioFlo Port contains a “permanent and non-eluting polymer that is ‘blended’ into the polyurethane from which the catheter is made” (Navilyst Medical, Inc., 2014, pg. 3). Navilyst Medical, Inc., the manufacturer

of the BioFlo Port claims that this port has 96% less thrombus accumulation on the surface of the catheter as compared to the non-coated conventional port catheters. However, the data supporting this claim is from in-vitro studies. Materials from Navilyst Medical, Inc., state that this technology provides a saline-only flushing option but does not specifically state that use of heparinized saline in the flushing protocol is not needed. Additionally, no studies on human patients have been conducted evaluating the rate of occlusions among patients with a BioFlo Port catheter. The implanted port-catheters in use by patients in the study currently in progress within the TriHealth Infusion Centers are made of a different material, thus the efficacy of flushing solutions in those catheters cannot be extrapolated to BioFlo Port. The desired outcome of the studying flushing solutions for implanted port- catheters is to change practice, (i.e., policy and procedure related to care of all implanted port-catheters) if appropriate. Therefore, another randomized control trial using the same methodology among patients with the BioFlo Port is needed.

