Participants in the control group will have yellow colored data collection Face Sheets while participants in the intervention group will have blue colored data collection Face Sheets. The Record of Flushes sheet will be white for patients in both groups. A blue or yellow sticker will be placed on the cover of the patient folder housed in treatment center noting the patient's involvement in the study. The data collection Face Sheet and the current Record of Flushes sheet will be kept in the individual patient folder as long as they remain a participant in the study. As the Record of Flushes data sheet becomes full, they will be collected by study staff and placed in locked drawer in a TriHealth office.

Experimental Aspect of the Study:

Patients who agree to participate in this study will be randomized to either the control group or intervention group as explained above.

Participants in the control group will have their implanted port catheters flushed according to the established TriHealth Nursing Policy: Venous Access Devices (VAD): Care and Maintenance (see Appendix A). Following the use of the port catheter with no continuous fluids running, or before de-accessing a port catheter (removing the port needle), the port will be flushed with 20 ml of normal saline and 5 ml of heparinized saline in the concentration of 100 units of heparin per mL.

Participants in the intervention group will have their ports flushed with normal saline only. That is, following the use of the port catheter with no continuous fluids running, or before de-accessing a port catheter (removing the port needle), the port will be flushed with 20 ml of normal saline. Turbulent flushing technique (the solution is injected using a push/pause technique every 1 mL) will be used in both groups and all accessed port catheters will have a neutral displacement connector. The MicroCLAVE® Clear displacement connector (ICU Medical, Inc., San Clemente, CA, USA) is the current product in use. Participants in both groups will be seen in a TriHealth Cancer Institute Infusion Center at a frequency consistent with their individual treatment plan and as outlined in the TriHealth

Nursing Policy: Venous Access Devices (VAD): Care and Maintenance (see Appendix A). Participants will remain in the study for 12 months or until they experience one of the potential risks noted below. Participants will be considered as having completed the study if they participate for 12 months.

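### The planned comparison of occlusion by flushing frequency does not test whether the saline-heparin difference depends on frequency; one interaction term in the planned regression would

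*Combined protocol and SAP*

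**What the plan says.** The Statistical Analysis section has three relevant parts.

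- Arms are compared on the dependent variables with "t-test, Chi-Square or Fisher's exact test as appropriate for the level of data under analysis".
- "Regression analysis will be used to determine the effect of the moderating variables on the occurrence of occlusion in the implanted ports". The moderating variables listed under Data Collection include "Number of times port flushed per month or frequency of flushing".
- The "control group and intervention group will be further stratified based on frequency of port flushing", after which "Differences in the rate of occlusion between stratified groups will also be calculated".

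For the third part the plan gives no number of strata, cut-points, named contrast, test, alpha, interaction term or exploratory label.

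The power analysis (under Recruitment) concerns one overall comparison against a difference of 0.10: "one-sided .05 significance level, a sample size of 198 participants per group will have 80% power". The Null Hypothesis section likewise states one hypothesis, on the overall occlusion rate. Under Experimental Aspect of the Study, participants attend "at a frequency consistent with their individual treatment plan", so flushing frequency is neither randomised nor fixed by the protocol. The Purpose of Study section says that the desired outcome "is to change practice, (i.e., policy and procedure related to care of all implanted port-catheters) if appropriate".

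**The concern.** Comparing occlusion between arm-by-frequency groups invites the reader to judge saline separately at low and at high flushing frequency. Separate results cannot show that the flush effect differs between strata. One stratum can reach significance and another miss it when the true difference is the same in both. That claim needs a direct test of the difference between differences.

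The planned regression does not fill the gap. As worded it estimates the effect of flushing frequency on occlusion, which is a main effect.

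Actual flushing frequency also accrues after randomisation. Groups formed on it are not baseline subgroups, and the randomised comparison is not guaranteed to hold within them.

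The stake is interpretive. A chance difference in one stratum could be taken as a real frequency effect, or a non-significant result in a small stratum could be taken as evidence that saline is adequate there.

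**Working it through.** **Inputs from the protocol (power analysis):** 198 per arm, 20% occlusion on standard treatment, margin 0.10, one-sided 0.05, 80% power.

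**Assumptions, because the protocol is silent:** k = 2, 3 or 4 equal strata; two-sided 0.05 for each within-stratum test; 20% occlusion in every cell unless stated.

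**1. The plan's own figure.** n = 2(0.2)(0.8)(1.645 + 0.842)² / 0.10² = 197.8, so 198 per group. It reproduces, for one overall comparison.

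**2. False saline-heparin differences within strata.** The strata are independent, so the chance of at least one is 1 − 0.95^k.

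| Strata | Formula | Simulation (40,000 trials, chi-square) |
|---|---|---|
| 2 | 9.8% | 9.7% |
| 3 | 14.3% | 13.7% |
| 4 | 18.5% | 19.4% |

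If only false differences in one given direction count, 1 − 0.975^k gives 4.9%, 7.3% and 9.6%. In the same simulation a single test of heterogeneity across strata rejected in 5.1%, 5.3% and 5.8% of trials.

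**3. Power against the 0.10 margin within a stratum.** With equal true rates, power = Φ(0.10/SE − 1.645), where SE = √(0.32/m) and m = 198/k per arm.

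- k = 2: m = 99, SE = 0.0569, Φ(0.114) = 54.5%
- k = 3: m = 66, SE = 0.0696, Φ(−0.209) = 41.7%
- k = 4: m = 49.5, SE = 0.0804, Φ(−0.401) = 34.4%

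**4. Why separate tests do not show effect modification.** Suppose the true rates are 20% v 30% in every stratum, so that frequency changes nothing. This scenario is hypothetical. For two strata the power of each two-sided 0.05 test is Φ((0.10 − 1.96√(2 × 0.25 × 0.75/99)) / √((0.16 + 0.21)/99)) = Φ(−0.34) = 36.8%. The two strata then disagree on significance in 2(0.368)(0.632) = 47% of trials. With three strata the power is 26.2% each, and disagreement is 1 − 0.262³ − 0.738³ = 58%.

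**5. What the interaction test can detect.** For two equal strata at 20%, the difference of differences has SE = √(2 × 0.32/99) = 0.0804. Detecting it with 80% power at two-sided 0.05 needs (1.960 + 0.842) × 0.0804 = 0.225, for example differences of 0 in one stratum and 22.5 percentage points in the other.

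**The case against.** The strongest reply is that the text promises only to calculate differences. It attaches no alpha, decision rule or claim to them, and the comparison may be descriptive. The hierarchy is also clear in substance: there is one stated hypothesis, one powered comparison, no research question on frequency, and frequency is listed as a moderating variable. The regression is already planned, so the gap is one unspecified term. All of this stands, and it lowers the severity. It does not supply the missing interaction, and a descriptive set of stratum rates invites the same misreading.

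Four stronger readings are tempting, and the documents do not support them.

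- **Testing at full alpha.** A reader may infer this because the sentence on stratified groups follows the list of tests. It is an inference; the only alpha in the protocol belongs to the overall power analysis.
- **Spurious findings are likely.** A chance of 10% to 19% is inflated but not likely. About 50%, ten times nominal, arises only if all 28 pairs among 8 cells are tested, and most of those pairs do not compare the two flushes at the same frequency.
- **Strata will usually disagree by chance.** With no true difference, two strata tested at 0.05 disagree in 2(0.05)(0.95) = 9.5% of trials. Applying the 0.10 margin inside strata gives 2(0.545)(0.455) = 50% for two strata and 1 − 0.417³ − 0.583³ = 73% for three, but no section proposes doing so.
- **A frequency-specific heparin rule will follow.** The Background section describes the same solutions and volumes for ports not in use. The stated aim concerns all implanted ports, and participants must be on active treatment at entry.

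**Conclusion.** The point holds in limited form. The plan sets out to look at occlusion by arm and flushing frequency but specifies nothing that tests whether the saline-heparin difference varies with frequency. The figures in steps 2 and 3 of the working show that individual stratum results would be weak evidence either way. They are illustrations, because they rest on assumed equal strata, a uniform 20% rate and an assumed two-sided 0.05 for the step 2 tests.

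A reader might go further and infer that the non-inferiority conclusion is in doubt. It is not: the overall comparison and its sample size do not depend on this analysis. This is a cheap improvement of low severity.

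**What to change.** In the Statistical Analysis section, replace the comparison of stratified groups with the following.

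1. In the regression already planned, include arm, flushing frequency and arm-by-frequency interaction. State the scale; the risk-difference scale matches the margin.
2. Base frequency on the treatment plan at enrolment, and fix any cut-points before outcome data are examined.
3. Report the saline-minus-heparin risk difference with a confidence interval in each stratum, and the single interaction test.
4. Label the analysis exploratory. State that non-inferiority is decided only by the overall difference against the 0.10 margin.

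**Cost.** A few sentences and one model term, with no extra participants. Planned frequency is not among the Face Sheet items described under Data collection tool. It would have to come from the chart, with one Face Sheet item added if it is not already recorded (the form itself is not in the documents available). Stratum-specific claims are given up. The interaction test has low power and will detect only large effect modification, so a non-significant result must not be read as proof that frequency does not matter.
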